4.13.10. Investigator-Confirmed Hereditary Angioedema (HAE) Attacks that involves the larynx

For exploring the dosing effect on laryngeal attacks, the time-normalized Investigator-confirmed HAE attacks that involves the larynx (per every-4-week) will be summarized by treatment group and compared between treatment group and pooled placebo group using a Poisson regression model and Pearson chi-square scaling of standard errors to account for potential overdispersion on the FAS. The model will include fixed effect for treatment group (categorical), baseline (the time-normalized run-in period attack rate, continuous), and the treatment-by-baseline interaction as covariates, and the logarithm of time in every-4-week that each patient was observed during the interested periods will be used as an offset variable.

Analyses on 2 interested periods will be performed, including from Week 1 to Week 25 and from Week 5 to Week 25. Number of patients and percentage per treatment group will also be summarized.

TP-GDO-WW-016-08 CONFIDENTIAL Project Document Version No. 2.0 Effective Date: 26 Nov 19 Project Document Effective Date: 13 Dec 2023 Related to: SOP-GDO-WW-019 Page 53 of 61

4.13.11. **Angioedema Activity Score (AAS)**

The AAS is a PRO measure developed to assess disease activity in patients with recurrent angioedema, which includes patients with HAE (Weller et al. 2013). The AAS consists of an opening question as well as 5 questions regarding the swelling episodes.

Opening question is "Have you had a swelling episode in the last 24 hours?" It may be used to count the number of angioedema affected days during the AAS documentation period but has no score.

5 questions regarding the swelling episodes will be summed up for AAS score calculation. A score between 0 and 3 points is assigned to every question as None = 0 and increase the point from 1 to 3 per severity for each question. The question scores are summed up to an AAS daily score. The daily AAS is summed up to AAS7 and AAS28. Calculation is described as the following: taking the first dose date/time as the start point, sum of daily AAS score during each period divided by the number of days contributed to that period multiplied by 7 days as AAS7 or multiplied by 28 days as AAS28. The minimum number of days for a valid AAS7 and AAS28 is 4 days per week and 3 weeks per 28 days, respectively. Accordingly, the minimum and maximum possible AAS scores are 0–15 for AAS daily score, 0–105 for AAS7, and 0–420 for AAS28.

AAS28 will be compared between ISIS 721744 80 mg every 4 weeks (or every 8 weeks) and pooled placebo using the MMRM model based on the FAS. The MMRM model will include effects of treatment, time, treatment-by-time interaction, and baseline value. The unstructured covariance model will be used to model the within patient errors, shared across treatment and small sample adjustments to standard errors and tests will be made following the Kenward-Roger approach (Kenward and Roger 1997).

AAS scores will be listed in by-patient listings.

4.14. **Other Analyses**

Psychometric analyses will be conducted for selected PRO assessments. Details will be specified in a separate analysis plan.

4.15. **Determination of Sample Size**

The power and sample size estimations were calculated using simulations based on a generalized linear model for count data assuming a Poisson distribution. The primary endpoint is the time-normalized number of Investigator-confirmed HAE attacks (per every-4-week) from Week 1 to Week 25. Assuming an HAE attack rate of 13.26 attacks per 6-month period in the placebo group and an HAE attack rate of 1.38 attacks per 6-month period in the ISIS 721744 80 mg every 4 weeks group, the sample size of 54 patients (2:1 ratio [ISIS 721744 : placebo]) will provide at least 90% power for the primary endpoint, with a 0.05 significance level. A total of approximately 84 patients (42 in the ISIS 721744 every-4-weeks group, 21 in the pooled placebo group, and 21 in the ISIS 721744 every-8-weeks group) will be enrolled in this trial to account for potential early dropouts and to facilitate some general safety evaluations.

TP-GDO-WW-016-08 **Project Document Version No. 2.0 CONFIDENTIAL** Effective Date: 26 Nov 19 **Project Document Effective Date:** 13 Dec 2023

4.16. Changes in the Conduct of the Study or Planned Analysis

The FAS represents the practically feasible intent-to-treat (ITT) population as delineated in International Conference on Harmonization (ICH) Guideline E9. This SAP choose to use FAS for the primary analysis of efficacy.

Responder analyses will be performed by using logistic regression with baseline and the interaction of baseline and treatment groups as covariates, if specified in the SAP. Compare to the Chi-square requested in the protocol, adjustment for baseline related covariates will generally reduce the variability of estimation of treatment effects and thus lead to more powerful hypothesis testing.

Rather than checking the distribution difference between treatment groups as ordinal variables by using a proportional odds model, PGIC and PGIS will be dichotomized to "better" and "no change or worse" and be analyzed for treatment effect by using logistic regression model. Additionally, the change from baseline on PGIS at each visit will be checked for the mean difference as continuous variable by using Wilcoxon Rank Sum test.

TP-GDO-WW-016-08 **Project Document Version No. 2.0** CONFIDENTIAL Effective Date: 26 Nov 19 **Project Document Effective Date:** 13 Dec 2023 Related to: SOP-GDO-WW-019

APPENDIX A. SAS SAMPLE CODES

(1) Poisson Regression:

```
proc genmod data=adeff;
  class arm;
  model no_attks = arm baserate arm*baserate / dist=poisson link=log offset=logmon pscale;
  lsmeans arm/ diff cl exp ilink;
run;
```

where

arm is treatment arm (i.e., ISIS 721744 80 mg every 4 weeks, ISIS 721744 80 mg every 8 weeks and pooled placebo);

no attks is number of Investigator-confirmed HAE attacks during the treatment period; baserate is time-normalized Investigator-confirmed HAE attack rate during the run-in period; logmon is logarithm of time in months each patient was observed during the treatment period.

(2) Negative Binomial Regression:

```
proc genmod data=adeff;
    class arm;
    model no_attks = arm baserate arm*baserate/ dist=negbin link=log offset=logmon;
    lsmeans arm/ diff cl exp ilink;
run;
```

where

arm is treatment arm (i.e., ISIS 721744 80 mg every 4 weeks, ISIS 721744 80 mg every 8 weeks and pooled placebo);

no_attks is number of Investigator-confirmed HAE attacks during the treatment period; baserate is time-normalized Investigator-confirmed HAE attack rate during the run-in period; logmon is logarithm of time in every-4-weeks each patient was observed during the treatment period.

CONFIDENTIAL

(3) Mixed Model with Repeated Measures (MMRM):

```
proc mixed /*scoring=4*/;
  class arm visit subject;
  model endpoint=arm baseline visit arm*visit arm*baseline/ ddfm=kr;
```

TP-GDO-WW-016-08 Effective Date: 26 Nov 19 Related to: SOP-GDO-WW-019 Project Document Version No. 2.0

Project Document Effective Date: 13 Dec 2023 Page 57 of 61

```
repeated visit / subject=subject type=UN;
lsmeans arm*visit / cl diff;
run;
```

where

arm is treatment arm (i.e., ISIS 721744 80 mg every 4 weeks, ISIS 721744 80 mg every 8 weeks and pooled placebo);

endpoint is change from baseline in AE-QoL total score/each domain score at Week 25;

baseline is baseline AE-QoL total score/each domain score;

visit is scheduled visit.

(4) Jump-to-Reference (J2R) for Recurrent Events:

Step 1a:

Draw a series of independent samples from the posterior distribution of model parameters using a Bayesian Poisson log-link model with an offset variable which holds the log of the exposure time for each patient.

```
proc genmod data = input_data;
  class arm;
  model no_attks = arm baserate arm*baserate /DIST= poisson LINK = log OFFSET = logmon;
  bayes outpost=bayes_out seed=721744 thin=n_thin nmc=n_draws nbi=n_bi;
run;
```

where

arm is treatment arm (i.e., ISIS 721744 80 mg every 4 weeks, ISIS 721744 80 mg every 8 weeks and pooled placebo);

no attks is number of Investigator-confirmed HAE attacks during the treatment period;

baserate is time-normalized Investigator-confirmed HAE attack rate during the run-in period;

logmon is logarithm of time in every-4-weeks each patient was observed during the treatment period;

n thin is the number of thinning parameters;

n draws is the number of draws;

n bi is the number of burn-in.

Step 1b:

According to the definition of J2R, the event rate in the active treatment arm is expected to shift to that of the reference arm. Post-withdrawal event rate in the reference arm is still under MAR.

TP-GDO-WW-016-08 CONFIDENTIAL
Effective Date: 26 Nov 19
Related to: SOP-GDO-WW-019

Page 58 of 61

Then calculate the unobserved event rate to sample the number unobserved events as the following:

rand('Poisson', exp(<unobserved event rate>)*<unobserved exposure period until the study end>

The imputed unobserved event numbers are added together with no attks (i.e., observed event numbers) to be the final total event numbers for patients who withdraw early from the study.

Step 2:

Analyze each imputed dataset using the designated statistical methods in previous sections (e.g., Poisson regression, etc.). Sample codes refer to other corresponding sections.

Step 3:

Combine the result by using PROC MIANYLIZE.

proc mianalyze;

modeleffects estimate;

stderr std err;

run;

where

estimate is the parameter estimate from Step 2;

std err is the standard error for the parameter estimate from Step 2.

(5) Tipping-Point Analysis for Recurrent Events:

First three steps are similar with (4) J2R for Recurrent Events multiple imputation mentioned above, expect for Step 1b being different:

Step 1b:

The unobserved event rate for both reference arm and active treatment arm is added by a series of shift parameter (denoted as δ). The number of unobserved events for each discontinued patient is then sampled as the following:

rand('Poisson', exp(<unobserved event rate $+\delta >$)*<unobserved exposure period until the study end>

Step 1b to Step 3 are repeated multiple times, each time with a different δ and thus multiple scenario results are generated.

TP-GDO-WW-016-08 **Project Document Version No. 2.0** CONFIDENTIAL **Project Document Effective Date:** 13 Dec 2023 Effective Date: 26 Nov 19 Related to: SOP-GDO-WW-019 Page 59 of 61

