Patients with the study termination date earlier than 25 weeks since the Study Day 1 will have two portions of treatment period, the pre-withdrawal part and the post-withdrawal part. Investigator-confirmed HAE attacks observed in the study will be combined with the imputed data to estimate the event rates for each treatment group. Missing data during the post-withdrawal part will be imputed by the following methods assuming J2R.

First, the Poisson regression model used for the primary analysis will be fitted to the data using a Bayesian approach, with non-informative priors for the mean and variance-covariance matrix to provide a joint posterior for the parameters in this model.

Second, Independent samples will then be drawn from the posterior distributions of model parameters fit using the Bayesian analysis. For each patient with missing data during the postwithdrawal part, these sampled values of the model parameters are then used to generate a set of values for the expected unobserved attack.

Last, the expected number of attacks for the post-withdrawal part is added to the number of attacks in the pre-withdrawal part to get the total number of attacks over treatment period for patients who have missing data.

TP-GDO-WW-016-08 **Project Document Version No. 2.0** CONFIDENTIAL Effective Date: 26 Nov 19 **Project Document Effective Date**: 13 Dec 2023

The post-withdrawal part of each pattern-specific distribution may be modelled using approaches discussed below:

Jump-to-Reference (J2R)

The J2R approach is an extremely conservative imputation approach that assumes that a patient receiving active Study Drug (ISIS 721744) does not sustain benefit after discontinuing study treatment. In J2R, missing event rate in both the ISIS 721744 treatment group and the pooled placebo group will be imputed by setting to the event rate of the pooled placebo group during the pre-withdraw part.

Tipping Point

The tipping point approach is known to progressively shift the imputed analysis results towards a point where the analysis conclusion is reversed (i.e., the analysis yields a nonsignificant p-value). The study adopts a two-way tipping point approach where a series of shift (denoted as δ) is applied to both active Study Drug (ISIS 721744) and placebo treatment arm. As the underlying distribution of primary endpoint is a Poisson distribution, the parameter of Poisson distribution (denoted as λ) is adjusted by δ as follows:

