 λ (ISIS 721744, tipping point) = λ (ISIS 721744, MAR-imputed) \times δ (ISIS 721744) λ (Placebo, tipping point) = λ (Placebo, MAR-imputed) \times δ (ISIS 721744)

The sequences of both λ starts at 1, where λ (ISIS 721744, tipping point) is increased by 0.25 upwards and λ (Placebo, tipping point) goes backwards to 0. The increment of 0.25 may be subject to adjust in case the tipping points are not yet to be discovered. The upper limit may expand further in case the 'tipping-point' that yields non-significant conclusion has not appeared yet. Under each combination of λ (ISIS 721744, tipping point) and λ (Placebo, tipping point), the same analysis method as Missing at Random (MAR) is applied to acquire the pvalue of the analysis. For example, if there are 6 numbers (from 1 to 2.25 by 0.25) set as δ, there should be in total 36 corresponding p-values in the whole tipping point analysis.

For each imputation method used, at least 100 imputed datasets will be generated.

Multiple Imputation Jump-to-Reference (J2R) – AECT Total Score and AE-QoL Total Score

The Markov Chain Monte Carlo (MCMC) method will be used under the multivariate normality assumption to impute the missing AE-QoL total score and AECT total score by treatment group. The variable list for imputations will include the baseline score, as well as all available post-baseline scores within the treatment period, in the order of protocol defined visits. The SAS procedure PROC MI will be used in the multiple simulation. EM algorithm will be used to derive a set of initial parameter estimates for MCMC method. A non-informative prior (Jeffreys' prior) will be used to derive the posterior distribution of the parameters. In case there are missing baselines, it will be imputed first by the average of available baselines across all patients in the FAS. In the case of non-monotone missing pattern, MCMC method will be used first so that each imputed data set has a monotone missing pattern based on the order of the variable list.

TP-GDO-WW-016-08 **Project Document Version No. 2.0 CONFIDENTIAL** Effective Date: 26 Nov 19 Related to: SOP-GDO-WW-019

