4.9.2.5. Sensitivity Analysis 4 – Tipping-Point Analysis

A tipping-point analysis will be conducted to measure the potential effect of missing data on the reliability of the primary efficacy analysis.

In this analysis, a range of progressively more conservative assumptions about the number of events occurring in the post-withdrawal period will be explored in order to find the assumption which will reverse the conclusion (i.e., yield a non-significant p-value) of the primary analysis. The assumption that will reverse the conclusion is referred to as the tipping point. Once the tipping point is identified, the clinical plausibility of the assumption can be assessed.

Missing event rate will be imputed by using the MI method described in Section 4.9.1.3. In each run, the Poisson regression model used for the primary analysis will be performed. Results will be combined using Rubin's rules.

The range of assumptions will be determined after treatment unblinding to ensure an appropriate range is explored based on the magnitude of treatment effect and pattern of missing data.

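### SAP tipping-point analysis: the placebo formula carries the active arm's shift, and the sample code uses one shift on a different scale, so neither runs the two-way grid described

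*Combined protocol and SAP*

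**What the plan says.** Protocol section 10.6.3.1 commits to a tipping-point analysis of the primary endpoint. The SAP specifies it in three places.

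- **Section 4.9.1.3 (Tipping Point).** "The study adopts a two-way tipping point approach", with shifts applied to the Poisson rate in each arm. The right-hand side of the placebo line is printed as "λ (Placebo, MAR-imputed) \times δ (ISIS 721744"); no placebo shift appears. Both sequences start at 1, "where λ (ISIS 721744, tipping point) is increased by 0.25 upwards and λ (Placebo, tipping point) goes backwards to 0". A p-value is obtained "Under each combination of λ (ISIS 721744, tipping point) and λ (Placebo, tipping point"). The worked example says that "if there are 6 numbers (from 1 to 2.25 by 0.25) set as δ, there should be in total 36 corresponding p-values".
- **Section 4.9.2.5 (Sensitivity Analysis 4).** Here "a range of progressively more conservative assumptions about the number of events occurring in the post-withdrawal period will be explored", using the imputation method of section 4.9.1.3. The tipping value is then to be judged for clinical plausibility. The range is to be set after unblinding.
- **Appendix A (5).** "The unobserved event rate for both reference arm and active treatment arm is added by a series of shift parameter (denoted as δ"). The count is drawn from a Poisson distribution whose mean contains exp(rate + δ). Then "Step 1b to Step 3 are repeated multiple times, each time with a different δ and thus multiple scenario results are generated".

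**The concern.** The prose calls for two separate shifts moving in opposite directions. The formula gives placebo the active arm's shift, the example lists only values of 1 or more, and the code shows one shift with no arm index and no crossing of arms. A shift common to both arms leaves the imputed rate ratio where it was, so it puts little pressure on the treatment contrast and may return no tipping value where the described analysis returns one.

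The scale also differs. A reported tipping value of 4 would be x4 on the text's scale and e^4, about x55, on the code's. Its clinical plausibility cannot be judged without knowing which applies.

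**Working it through.** **1. The plan's own count.** From 1 to 2.25 by 0.25 there are 6 values, and 6 x 6 = 36, as stated. This requires a separate shift in each arm; one shared shift gives 6 runs. All six values are 1 or more, so the example never takes placebo below its missing-at-random (MAR) rate. The placebo step is not stated. If it were also 0.25, the sequence 1, 0.75, 0.5, 0.25, 0 has 5 values and the grid 6 x 5 = 30 cells. With a step of 0.2 it has 6 values and 36 cells.

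**2. The rate ratio.** The planning rates (SAP 4.15) are 1.38 and 13.26 attacks per 6 months, a ratio of 1.38/13.26 = 0.104.

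- Shared shift: (1.38 δ)/(13.26 δ) = 0.104 for every δ, on either scale.
- Separate shifts, active x2.25 and placebo x0.25: 3.105/3.315 = 0.937.

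**3. The scale.** The text multiplies the rate by δ; the code multiplies it by exp(δ).

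| Value in the text | Multiplier in the text | Multiplier if entered in the code |
|---|---|---|
| 0 (placebo floor) | x0 | x1 |
| 1 (no shift) | x1 | x2.72 |
| 2.25 | x2.25 | x9.49 |
| 4 | x4 | x54.6 |

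With the text's placebo values from 1 to 0, the code's multiplier runs from 2.72 to 1, so placebo could not fall below MAR. The code can match the text for positive multipliers by entering log(δ), but the SAP does not say so, and a multiplier of exactly 0 has no finite logarithm.

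**4. Size, by simulation.** The documents do not give the missing exposure or the overdispersion, so these are assumed: 42 active and 21 placebo patients at the planning rates; dropouts missing half the period; gamma between-patient variance of 0, 0.5 or 1; a two-arm Poisson model with Pearson scaling and no covariate; results combined by Rubin's rules; 15 to 50 imputations and 300 to 800 runs per cell. The tip is the active multiplier at which the median test turns non-significant.

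| Dropouts active/placebo | Missing exposure, active/placebo | Tip, placebo x0 | Shared multiplier x1000, median z (absolute) |
|---|---|---|---|
| 4/2 | 4.8%/4.8% | 58-63 | about 2.2 |
| 8/4 | 9.5%/9.5% | 33-39 | about 3.2 |
| 16/8 | 19.0%/19.0% | 18-20 | about 4.9 |
| 4/4 | 4.8%/9.5% | 57-60 | about 3.1 |
| 8/2 | 9.5%/4.8% | 37-41 | about 2.0 |

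**5. Check of the shared column.** As the shared multiplier grows, imputed counts dominate. Let k be the multiplier times the half period. For 8/4 dropouts the dropout fraction is 4/21 in each arm:

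- Dispersion: (42 x 1.38 + 21 x 13.26)(17/21)k/61 = 4.46k.
- Poisson variance of the log ratio: [1/(8 x 1.38) + 1/(4 x 13.26)]/k = 0.109/k.
- k cancels, and z = ln(13.26/1.38)/sqrt(4.46 x 0.109) = 2.263/0.699 = 3.24.

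The same formula gives about 2.2 for 4/2 and 5.2 for 16/8. It leaves out between-imputation variance, which lowers the simulated values a little. The shared test therefore approaches a plateau above 1.96 in the equal-missing cases.

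**6. What the tips mean.** 18 x 1.38/13.26 = 1.9 and 63 x 1.38/13.26 = 6.6. Over the equal-missing cases, the active post-withdrawal rate at the tip is 1.9 to 6.6 times the planned placebo rate. At the example's largest value, 2.25, every reading stays significant in at least 99.4% of runs in those cases.

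**The case against.** The strongest reply is that the intent is clear. The surrounding text is explicitly two-way, sends placebo down to 0, tests every combination and counts 36 p-values, so a programmer could not use a shared shift and still follow that section. On this view the placebo label is a typing slip. The appendix is sample code with placeholders, section 4.9.2.5 points to section 4.9.1.3 and not to the appendix, and a multiplier and a log-additive shift are equivalent once the logarithm is taken. The 30-cell count assumes a placebo step that the SAP does not state. The simulation omits the baseline and interaction terms and uses fewer than the 100 imputations required.

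Much of this stands. Separate shifts were intended, the code's form is a valid shift in itself, 6 x 6 = 36 is correct, and the simulation is only an illustration. But correcting the label leaves the code's single shift, the conflict over the no-shift value and the undefined placebo sequence. The appendix is the only place that shows how the shifted counts are drawn. Leaving the range until after unblinding does not settle the scale or the arm structure, and is a reason to fix both beforehand.

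**Conclusion.** The point holds and should be fixed. The formula, example and code as written do not carry out the two-way analysis the SAP describes, and text and code disagree on the value that means no shift. These findings rest on the wording alone.

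The effect on any p-value depends on missing exposure and overdispersion that the documents do not give. Under the assumptions above, a literal shared shift would leave the median test significant even at x1000 (only just, at about 2.0, when active has the greater missingness), while the described analysis tips at about 18 to 63. Those tips need active rates well above the planned placebo rate, so the planning-rate conclusion is not in question. The problem is confined to Sensitivity Analysis 4; the primary, negative binomial and jump-to-reference analyses are untouched.

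**What to change.** In section 4.9.1.3:

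- Write λ(Placebo, tipping point) = λ(Placebo, MAR-imputed) x δ(Placebo).
- Say that the sequences are values of δ, not λ, and that (1, 1) is the MAR cell.
- State the placebo step down to 0 and align the example: 36 cells with a step of 0.2, or 30 with 0.25.

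In Appendix A (5):

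- Index δ by arm and cross the two sequences.
- Draw Poisson(exp(log rate) x δ_arm x unobserved time), which also handles δ = 0.

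Report tipping values as rate multipliers. The cost is one corrected formula, a sentence or two on the sequences and example, and a few lines of sample code.
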